| Table 4 | Sample size, event rate and probability | 25 |
| Table 5 | 95% CI on the percentage of participants with event(s) of interest | 26 |

LIST OF FIGURES

| | PAGE |
|---|-------------|
| Figure 1 Overall Study design overview | 9 |
| Figure 2 Study design overview- Prospective cohort..... | 10 |

VERSION HISTORY

| SAP Version | Approval Date | Protocol Version (Date) on which SAP is Based | Change | Rationale |
|-----------------|------------------|---|---|---|
| SAP | 20 January 2023 | Protocol Amendment 1 (17 January 2023) | Not Applicable | Original version |
| SAP Amendment 1 | 13 July 2023 | Protocol Amendment 2 (21 June 2023) | Remove unnecessary analysis sets. CCI  Provide analysis plan for SRT safety monitoring. | Revised for Protocol Amendment 2 and Health Authority requests. |
| SAP Amendment 2 | 16 December 2024 | Protocol Amendment 2 (21 June 2023) | | Addition of subgroup analyses as per Health Authority request. |
| SAP Amendment 3 | 17 Feb 2025 | Protocol Amendment 2 (21 June 2023) | Adjust methods section to distinguish between first and any pregnancy calculation methods Remove secondary endpoint: Incidence of selected pregnancy outcomes, pregnancy related AESIs and infant | To have the SAP aligned with the OPS |

| SAP Version | Approval Date | Protocol Version (Date) on which SAP is Based | Change | Rationale |
|-------------|---------------|---|---|-----------|
| | | | AESIs by risk status and by selected risk factors for or causes of those events/outcomes during any pregnancy conceived within 2 years post-vaccination in participants enrolled in RSV MAT studies (by study arm, those previously received RSVPreF3 and control) up to Day 42 post-delivery. | |

1. INTRODUCTION

The purpose of this SAP is to describe the planned analyses to be included in the CSR for Study 219510 (RSV MAT-015). Details of the planned analysis, as well as the final analyses, are provided.

[figure not shown]
1.1. Objectives, Estimands and Endpoints

Table 1 Study objectives, estimands and endpoints

[figure not shown]
| Objectives | Endpoints & Estimands |
|---|--|
| Primary | |
| To describe the incidence of pregnancy outcomes, pregnancy related adverse events of special interest (AESIs) and infant AESIs during the first pregnancy conceived within 2 years post-vaccination in participants enrolled in RSV MAT studies (by study arm, those previously received RSVPreF3 and control) up to Day 42 post-delivery. | Incidence of pregnancy outcomes, pregnancy related AESIs and infant AESIs during the first pregnancy conceived within 2 years post-vaccination in participants enrolled in RSV MAT studies (by study arm, those previously received RSVPreF3 and control) up to Day 42 post-delivery. |
| Secondary | |
| To describe the incidence of pregnancy outcomes, pregnancy related adverse events of special interest (AESIs) and infant AESIs during any pregnancy conceived within 2 years post-vaccination in participants enrolled in RSV MAT studies (by study arm, those previously received RSVPreF3 and control) up to Day 42 post-delivery. | Incidence of pregnancy outcomes, pregnancy related AESIs and infant AESIs during any pregnancy conceived within 2 years post-vaccination in participants enrolled in RSV MAT studies (by study arm, those previously received RSVPreF3 and control) up to Day 42 post-delivery. |
| To describe the incidence of selected pregnancy outcomes, pregnancy related AESIs and infant AESIs by risk status and by selected risk factors for or causes of those events/outcomes during pregnancies conceived within 2 years post-vaccination in participants enrolled in RSV MAT studies (by study arm, those previously received RSVPreF3 and control) up to day 42 post-delivery. | Incidence of selected pregnancy outcomes, pregnancy related AESIs and infant AESIs by risk status and by selected risk factors for or causes of those events/outcomes during the first pregnancy conceived within 2 years post-vaccination in participants enrolled in RSV MAT studies (by study arm, those previously received RSVPreF3 and control) up to Day 42 post-delivery. |
| Tertiary (Exploratory) | |

CCI

1.2. Study Design

Overview of Study Design and Key Features

Figure 2 Study design overview- Prospective cohort

*Contacts every 6 months up to 2 years (+2 months) post-vaccine/control (received as part of prior RSV MAT study participation), unless a pregnancy conceived post-vaccine/control is reported.

** Once a pregnancy is reported, the participant is followed monthly during pregnancy until delivery, then again at Day 42 post-delivery. Pregnancy follow-up will include all pregnancies ongoing at enrolment or newly conceived during follow-up within 2 years post vaccine/control. If Day 42 post-delivery is <2 years+2 months, the woman returns to contacts every 6 months until 2 years (+2 months) post-vaccine/control.

***In addition to the planned study contacts, additional unplanned visits or medical procedures can be done as per the investigator's discretion.

Design Features

Study Type: A safety follow-up cohort study of interventional clinical trials.

Experimental design: Phase IIIB, non-randomized, open label, multi-country, cohort study to describe the safety of study participants who received RSVPreF3 maternal vaccination (any dose) or controls from previous RSV MAT studies

Study Population: All study participants from RSV MAT studies who have received either RSVPreF3 vaccine or control (placebo, Tdap only, influenza vaccine only) will be eligible to be included in this study.

Duration of the study: The study period starts from the date of start of any pregnancy conceived after RSV MAT vaccination (RSVPreF3) or control vaccination in RSV MAT studies or from the date of current study enrollment, whichever date is earlier. The study period ends at current study enrollment for retrospective cohort participants. The study period ends at 2 years+2 months post vaccine/control for prospective cohort participants who are not pregnant at 2 years post vaccine/control. The study period ends at Day 42 post-delivery for prospective cohort participants who are pregnant at 2 years post vaccine/control or who are pregnant at enrollment.

Study intervention

Not applicable.

Study intervention

Not applicable.

Assignment

| Overview of Study Design and Key Features | |
|---|---|
| Concomitant Therapy | Not applicable. |
| Interim Analysis | Not applicable. |
| End-of-study definition | The participant has completed all periods of the study including the last contact (study conclusion). |

2. STATISTICAL HYPOTHESES

No statistical hypotheses will be tested. All statistical analyses are descriptive.

2.1. Multiplicity Adjustment

No statistical multiplicity adjustment will be performed.

3. ANALYSIS SETS

Table 2 Maternal Participants

| Analysis Set | Definition / Criteria | Analyses Evaluated |
|-------------------------|---|---------------------------------------|
| Screened | All participants who were screened for eligibility. | Study Population |
| Enrolled | All maternal subjects who completed the informed consent process and signed the informed consent form and were determined eligible for study participation. Note screening failures (who never passed screening even if rescreened) are excluded from the Enrolled analysis set as they did not enter the study. | Study Population |
| Full Analysis Set (FAS) | All maternal subjects who had pregnancy defined by this study (defined in the Protocol Section 5.1). | Primary, Secondary and other analyses |

Table 3 Infant Participants

| Analysis Set | Definition / Criteria | Analyses Evaluated |
|-------------------------|--|---------------------------------------|
| Enrolled Infant | Infants live-born to the maternal set, whose parents/LARs completed the informed consent process and signed the informed consent form. | Study Population |
| Full Analysis Set (FAS) | All infant subjects in the infant set who have post-delivery/birth data. | Primary, Secondary and other analyses |

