^a Any study contact may be via telephone, SMS, email, video-telephone/telemedicine or other means, depending on local best practice. If the study site is the participant's primary healthcare facility, contact with study personnel may also be made in the context of a visit for routine or event-driven care.

^b May be combined with another contact where pregnancy is first reported [e.g., combined with Visit 1/Contact 1 (for past/ongoing pregnancies at enrollment), follow-up contact, unscheduled contact.]

^c For participants who are not pregnant at 2 years post vaccine/control, the study conclusion will be completion of the last bi-annual contact, at least 2 months after 2 years post-vaccine/control. If the participant is pregnant at 2 years post vaccine/control **or at study enrollment**, study conclusion will be completion of Day 42 post-delivery. **WONCBP at study enrollment, or recipient of bilateral tube ligation prior to study enrollment will be excluded from the study if she has not conceived a pregnancy post-vaccine/control and does not plan to use any additional measures to attempt to conceive a pregnancy (e.g., sterilization reversal or in vitro fertilization (IVF)).**

^d Any SAEs assessed as related to study participation (e.g., protocol-mandated procedures) or related to a GSK product will be recorded from the time a participant consents to participate in the study.

Table 3 Schedule of Activities for prospective cohort – Infant participant

Type of contact ^a	Delivery ^b	Day 42 Contact ^b	Notes
Timepoints	Day 1	Day 42	
Informed consent	•		Infant informed consent is anticipated at delivery, but may be done at any time up to the delivery contact if allowed at the site (or at Visit 1/Contact 1 for an infant born from a past pregnancy)
Inclusion and exclusion criteria	•		
Demography and lifestyle characteristics	•	•	Demography at birth, and lifestyle at Day 42 post-delivery
Contact information for all HCPs seen by infant from birth through Day 42	○	○	
Safety assessments (from medical record review)			
Record medications/vaccinations	•	•	
Record medically attended AEs until Day 42	•	•	
Infant AESIs from birth until Day 42	•	•	
Infant SAEs from birth until Day 42	•	•	
Record SAEs related to study participation or related to a GSK product ^c	•	•	
MAEs, SAEs and AEs (AESIs) leading to study withdrawal	•	•	
Final Activities			
Study conclusion		•	

• Is used to indicate a study procedure that requires documentation in the individual eCRF.

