5.1. Inclusion criteria

5.1.1. Retrospective cohort

Adult/Adolescent Participant:

- Adult/Adolescent study participant, from *any of the prior RSV MAT* studies who have either received RSV MAT vaccine or control (placebo, Tdap or influenza vaccine).
- Study participant:
 - Who has reached 2 years+2 months post vaccine/control prior to/at enrollment or
 - who has not reached 2 years+2 months post vaccine/control prior to/at enrollment but is a Woman of Nonchildbearing Potential (WONCBP) as defined in Section 10.3.1.2 at study enrollment, or recipient of bilateral tubal ligation prior to study enrollment.
- Study participant with any pregnancy conceived post-vaccination/control, that has reached Day 42 post-delivery prior to/at enrollment.
- Provide signed and dated informed consent form.
- Be willing to comply with all study requirements and be available for the duration of the study.

Infant Participant:

- Participant live born as the result of a pregnancy followed in an adult/adolescent participant in this study.
- Signed and dated informed consent form obtained from the participant's parent(s)/LAR(s) prior to performance of any study-specific procedure.

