- An *uncomplicated* vaginal delivery or planned cesarean section *expected* to occur in a hospital setting should NOT be reported as an AE, MAE or SAE.
- A medical *complication* that requires a cesarean section or an emergency induction may be reported as an SAE/AESI (as applicable), using the corresponding Expedited AE report form.

8.4.8.2. Reporting of congenital anomalies in relation to pregnancy outcomes and SAEs and/or AESIs

Table 9 summarizes the requirements for AESI/SAE reporting of adverse pregnancy outcomes when congenital anomalies are/are not present.

Table 9 Reporting pregnancy outcomes with or without congenital anomalies as AESIs and/or SAEs

	Live birth		Fetal death /stillbirth		Elective / Therapeutic Termination	
	AESI	SAE	AESI	SAE	AESI	SAE
None	-	-	-	X	-	X
Major ¹	X	if reportable per MACDP ³	-	X	-	X
Minor ²	-	if reportable per MACDP ³	-	X	-	X

* In the event of infant's participation in the study, congenital anomalies are to be reported in the infant's eCRF.

However, when there is no live birth, or no signed informed consent for the infant or the congenital anomaly is being reported for a subsequent pregnancy, it will be encoded in the maternal participant's eCRF.

¹Structural or functional defects that require surgical and/or medical treatment and that have serious adverse effects on health or development (functional) or have significant cosmetic impact.

²Anatomic variants or defects that do not have serious medical, functional or cosmetic consequences for the child.

³Metropolitan Atlanta Congenital Defects Program (MACDP) 6-Digit Code Defect List

Additional guidance when congenital anomalies are present are as follows:

The term “congenital anomaly” is broad. GSK uses the case definitions provided in the Centers for Disease Control and Prevention (CDC) Metropolitan Atlanta Congenital Defects Program guidelines, with specific reference to the MACDP 6-Digit Code Defect List [MACDP, 2021] to ensure that the collection and recording of these data is complete and consistent across studies and projects.

To report a pregnancy outcome of live birth with congenital anomaly as an SAE per these guidelines, an infant must have a birth defect that is *included in MACDP surveillance data* per the MACDP 6-Digit Code Defect List. (Congenital anomalies that are not included in MACDP surveillance data may be reported as medically attended or serious adverse events, if appropriate).

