9.3. Statistical analyses

9.3.1. General considerations

All statistical analyses are descriptive. Besides the primary analyses, sub-group analyses may be conducted.

All primary and secondary analyses will be performed on the ***Full Analysis Set***.

9.3.2. **Primary endpoints analysis**

	Primary Endpoints	Statistical Analysis Methods
Maternal participants	Number and percentage of maternal participants reporting pregnancy outcomes and pregnancy related AESIs within the first pregnancy conceived within 2 years post-vaccination in participants enrolled in prior RSV MAT studies up to Day 42 post-delivery.	The number and percentage of maternal participants reporting pregnancy outcomes and pregnancy related AESIs within the first pregnancy conceived within 2 years post-vaccine/control will be tabulated with its exact 95% CI by study arms. By participant listings of pregnancy related outcomes and AESIs will be prepared
Infant participants	Number and percentage of infant participant reporting infant AESIs from the first pregnancy conceived within 2 years post-vaccination in participants enrolled in prior RSV MAT studies up to Day 42 post-delivery.	The Number and percentage of infant participant reporting infant AESIs from the first study pregnancy conceived within 2 years post-vaccine/control will be tabulated with its exact 95% CI by study arms. By participant listings of infant AESIs will be prepared.

Pregnancy outcomes include (not limited to) spontaneous abortion, stillbirth, and preterm birth. The pregnancy related adverse events of special interest (AESIs) and infant AESIs are listed in Section 8.4.5.1.

9.3.3. **Secondary endpoints analyses**9.3.3.1. **Pregnancy outcomes and AESIs from any study pregnancy**

	Secondary Endpoints	Statistical Analysis Methods
Maternal participants	Number and percentage of maternal participants reporting pregnancy outcomes and pregnancy related AESIs during any study pregnancy conceived within 2 years post-vaccination in participants enrolled in prior RSV MAT studies up to Day 42 post-delivery.	The number and percentage of maternal participants reporting pregnancy outcomes and pregnancy related AESIs during any pregnancy conceived within 2 years post-vaccination in participants enrolled in prior RSV MAT studies up to Day 42 post-delivery , will be tabulated with its exact 95% CI by study arms on subject level. By participant listings of pregnancy related outcomes and AESIs will be prepared.

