4.2.1. Definition of primary endpoints

The first pregnancy during study period is defined as the first pregnancy conceived post-vaccination or control in participants enrolled in RSV MAT studies (those previously received RSVPreF3 or control) up to Day 42 post-delivery.

Pregnancy outcomes include (not limited to):

1. Live birth
2. Spontaneous abortion

3. Stillbirth
4. Elective/therapeutic termination
5. Live birth Congenital anomaly(ies)
6. Spontaneous abortion Congenital anomaly(ies)
7. Fetal death/still birth Congenital anomaly(ies)
8. Elective/therapeutic termination Congenital anomaly(ies)

| Pregnancy-related AESIs | Infant AESIs |
|---|--|
| 
 • Hypertensive disorders of pregnancy: 
 – gestational hypertension, – pre-eclampsia, – pre-eclampsia with severe features including eclampsia; • Fetal growth restriction; • Pathways to preterm birth: 
 – premature preterm rupture of membranes, – preterm labor, – insufficient cervix – provider-initiated preterm birth; • Gestational diabetes mellitus; and • Chorioamnionitis. | 
 • Small for gestational age, • Low birth weight including very low and extremely low birth weight (<2500 g, <1500 g, <1000 g), • Congenital anomalies: 
 – major external structural defects, – internal structural defects, – functional defects, • Neonatal death 
 – in a non-viable live birth [<22 weeks gestation] – in an extremely pre-term birth [22.GA<28 weeks], – in a preterm live birth [28.GA<37 weeks], – in a term live birth, • Preterm birth |

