4.2.2. Main analytical approach

All primary analyses will be performed on the Full Analysis Set.

Main primary analyses in maternal participants will include summaries of pregnancy outcomes and pregnancy related AESIs overall and by study arms. Pathways to preterm birth will be further broken down as: extremely preterm births (GA at birth: < 28 weeks); very preterm births (GA at birth: 28 - < 32 weeks); moderate to late preterm births (32 - < 37 weeks).

Main primary analyses in infant participants will include summaries overall, by study arms and by gestational age at birth (≥ 37 weeks or < 37 weeks; overall) of infant AESIs.

Primary endpoints will be reported by study arms while stratified by **CCI**

Pregnancy outcomes analytical approach:

The number and percentage of each pregnancy outcome is calculated among the maternal Full Analysis Set (for participants with medical records available), per pregnancy regardless of the number of fetuses in the concerned pregnancy.

The pregnancy related adverse events of special interest (AESIs) analytical approach:

The number and percentage of each pregnancy related adverse event of special interest is calculated based on the number of pregnancies reporting the symptom at least once. In addition, we will report the occurrence of pregnancy related adverse events of special interest. Only pregnancies based on medical record collection will be considered.

For infant participants, the infant participant reporting AESIs analytical approach:

The number and percentage of each neonatal adverse event of special interest is calculated based on the number of infants reporting the symptom at least once. In addition, we will report the occurrence of neonatal adverse events of special interest. Infants' data based on medical records only, will be considered.

CCI

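### Neonatal death, and preterm birth as a defined endpoint, are analysed in the SAP only on infants with their own signed consent, and live births without that consent are not tabulated

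*SAP*

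**What the plan says.** SAP section 3 (Table 3) defines the Enrolled Infant set as "Infants live-born to the maternal set, whose parents/LARs completed the informed consent process and signed the informed consent form". The infant FAS is "All infant subjects in the infant set who have post-delivery/birth data". No set is defined under the name infant set; I read it as the Enrolled Infant set. SAP 4.2.1 places both preterm birth and neonatal death in the infant AESI column, and SAP 4.2.2 says each infant AESI "is calculated based on the number of infants reporting the symptom at least once".

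On timing, Protocol Table 3 says for the prospective cohort: "Infant informed consent is anticipated at delivery, but may be done at any time up to the delivery contact", where the site allows it. Protocol Table 4 lets the delivery contact fall anywhere from delivery to Day 42. In the retrospective cohort, maternal and infant consent are both taken at the single enrolment contact (Protocol Table 1).

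At maternal level, Protocol 9.3.2 states: "Pregnancy outcomes include (not limited to) spontaneous abortion, stillbirth, and preterm birth". The SAP 4.2.1 list, which opens "Pregnancy outcomes include (not limited to", gives eight outcomes and preterm birth is not among them. The maternal FAS has no infant-consent condition. On it, SAP 4.2.2 counts Pathways to preterm birth per pregnancy, split by gestational age at birth (<28, 28 to <32 and 32 to <37 weeks). SAP 6.1.2 summarises gestational age at birth (≥37 or <37 weeks) for mothers by arm.

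The protocol foresees infants without consent in one place, the footnote to Table 9 (section 8.4.8.2). The sentence that begins "However, when there is no live birth, or no signed informed consent for the infant or the congenital anomaly is being reported" sends the anomaly, in those cases, to the mother's eCRF. SAP 6.1.1 tabulates infants enrolled and withdrawn, nothing else.

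**The concern.** An endpoint should not be counted on a set whose membership can depend on that endpoint. Neonatal death is defined as death within 28 completed days of birth (Protocol Table 30), and infant consent may be sought up to Day 42. The whole event window can therefore close before the parents are asked. In the retrospective cohort the outcome is always known by then. If parents of an infant who died or was born very early sign less often, the infant-level rates are too low. If that tendency differs between arms, the contrast is distorted too. Participants know which arm they were in, and Protocol 4.5 already accepts that mothers with a previous adverse outcome may take part at different rates. The visible text has no counterpart for infant consent.

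The stakes are higher than for a routine safety table. An imbalance in preterm births is the signal that stopped vaccination in the programme (Protocol 2.2). Preterm birth is adjudicated (Protocol 8.3.1), and it is compared between arms with relative risks and p-values (SAP 4.3.2.2). The denominator that governs should be explicit.

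**Working it through.** **Where each outcome is counted**

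| Outcome | Maternal level, no infant consent needed | Infant level | Stated route if infant not consented |
|---|---|---|---|
| Preterm birth | Named in Protocol 9.3.2; in the SAP through Pathways and the gestational-age tabulation | Infant AESI | None named as such |
| Neonatal death | None stated | Infant AESI | None |
| Congenital anomaly | Live birth with anomaly (SAP 4.2.1) | Infant AESI | Mother's eCRF (Protocol Table 9 footnote) |

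Pathways is close to a preterm birth count but is not one. It comprises four separately defined conditions (Protocol Table 22). Insufficient cervix can be met by cerclage without preterm delivery. Preterm labor needs documented cervical change even at its lowest certainty level.

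**Inputs from the documents:** about 650 participants with a pregnancy, 300 as the lower scenario; planning event rate about 5%; lowest tabulated rate 0.5% (SAP section 5).

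**Inputs assumed, because the documents give none:** one live-born infant per pregnancy; consent c0 = 95% for unaffected infants; consent c1 for affected infants as shown; neonatal death rate 0.5% to 1%.

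1. *The plan's own figure.* P(at least one event) = 1 − (1 − p)^N. At p = 0.5%, 1 − 0.995^300 = 77.8% and 1 − 0.995^650 = 96.2%, matching the stated 78% and 96%. These use every pregnancy and make no allowance for infants lost through missing consent.

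2. *Rate seen in the consented set.* Observed = p·c1 / [p·c1 + (1 − p)·c0].
   - Death, p = 1%, c1 = 50%: 0.0050 / (0.0050 + 0.9405) = 0.53%.
   - Death, p = 1%, c1 = 70%: 0.0070 / (0.0070 + 0.9405) = 0.74%.
   - Preterm, p = 5%, c1 = 80%: 0.0400 / (0.0400 + 0.9025) = 4.2%. This applies to the infant-level table only.
   - With c1 = c0 the observed rate equals p and there is no bias.

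3. *Chance of recording any death.* 1 − (1 − p·c1)^N at p = 0.5%, c1 = 50%: 1 − 0.9975^300 = 53%, against 78% with every birth counted; 1 − 0.9975^650 = 80%, against 96%.

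4. *Expected deaths.* 650 × 0.5% = 3.25 and 650 × 1% = 6.5, so one or two unrecorded deaths would matter.

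5. *Arm contrast.* Take equal true rates of 5%, with consent for affected infants of 90% in one arm and 50% in the other. The observed rates are 0.0450/0.9475 = 4.75% and 0.0250/0.9275 = 2.70%, an apparent relative risk of 0.57 instead of 1.00. With 90% against 70% it is 0.79.

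**The case against.** The strongest reply is that preterm birth, the outcome behind the signal, already has a count that needs no infant consent. A reader might infer from the infant set that preterm birth is counted only in consented infants. The documents do not support that: Pathways is in the main primary analysis per pregnancy, including the <28-week group, and gestational age below 37 weeks is tabulated for mothers. The SAP's outcome list is also open-ended, so its silence does not strike preterm birth out. This stands. What remains is that the SAP gives no pregnancy-level preterm birth endpoint by name, and Pathways does not define one.

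A reader might also infer that infants who died drop out. That is not documented either. The inclusion criterion is "Participant live born as the result of a pregnancy followed in an adult/adolescent participant in this study", with similar wording for the prospective cohort, so an infant who died remains eligible. Consent may precede delivery where the site allows. The child-in-care exclusion concerns legal custody, not illness. In the retrospective cohort a bereaved mother may decline altogether; that is selection of mothers, which Protocol 4.5 acknowledges and which a change of infant denominator would not cure.

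The magnitudes rest on assumed consent and death rates. Even the illustrative 4.2% lies inside the plan's own interval of 3.5% to 7% for 5% among 650. That is fair as to size, but an interval for sampling error does not cover bias.

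Finally, SAP 4.2.3 on sensitivity analyses is blacked out, so nobody can say that an analysis of unconsented infants is absent.

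**Conclusion.** The point holds in a limited form. Neonatal death is listed only as an infant AESI, on a set that requires a separate consent which can follow the outcome, and no maternal-level route is stated for it. Preterm birth is partly protected by the maternal counts, but the SAP's listed pregnancy outcomes do not match Protocol 9.3.2. Live births without infant consent do not appear in the visible disposition plan, so a reader of the report could not judge whether selection occurred.

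Bias is a risk here, not a finding. It needs consent to depend on outcome, and, for the contrast, on outcome differently by arm. Its size cannot be derived from the documents; the 0.53% to 0.74% and the relative risk of 0.57 illustrate assumed consent rates and nothing more. The change is worth making because it is cheap and either removes the selection or makes it visible.

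**What to change.** - **SAP 4.2.1 and 4.2.2:** list preterm live birth (gestational age at birth <37 weeks) as a pregnancy outcome, counted per pregnancy on the maternal FAS, in line with Protocol 9.3.2. Keep the infant-FAS count as supportive.
- **SAP 6.1.1:** tabulate by arm the live births not enrolled as infants, with gestational age at birth and known outcome.
- **Neonatal death:** report it with all live births to the maternal FAS as denominator where the mother's record holds the outcome and maternal consent and local law allow. Keep the infant-FAS version beside it.

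The cost is SAP wording and some derivation from maternal data. There will be less infant detail for unconsented infants. The scope of maternal consent must be confirmed country by country. For neonatal death the sponsor must also check that the maternal eCRF captures survival, which the visible text does not show; if it does not, that item needs more than a SAP edit. The Table 9 footnote already accepts the maternal eCRF as the recording route for anomalies.
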